1.2 Study Aim and Objectives

The main aim of the pilot study aim is to assess the feasibility of immunizing newborns, within selected facilities, with BCG and OPV0 within 24 hours of birth by integrating routine immunization into maternity and early newborn care. In this study only the current birth vaccines (BCG and OPV) will be assessed. The findings will inform strategies for strengthening the birth platform as well as HepB-BD introduction which is envisaged in the cMYP (2016-2021).

Further, the specific objectives of this pilot study are to:

- 1. Integrate birth dose immunizations into facility-based maternity services
- 2. Measure the change in proportion of facility births receiving birth doses BCG and OPV0 within 24 hours
- 3. Measure the change in average age of all babies receiving birth doses of BCG and/or OPV0 at the facility
- 4. Assess the operational feasibility and acceptability of interventions and describe any factors (barriers and enablers) that may influence further implementation of birth dose strategies

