1.3 Justification for Pilot Study

Cameroon's national policy recommends that OPV0 and BCG be administered as soon as possible after birth. While coverage rates for BCG (84%) and OPV0 (79%)¹⁰ are relatively high in Cameroon, it is estimated that these vaccines are often administered weeks or months after birth,¹¹ not within the timeframe recommended for their administration or that which will be needed for a successful HepB-BD program (<24 hours after birth).¹² Currently, most health facilities do not administer vaccines every day, but rather only on designated immunization days. With babies being born every day, this poses a challenge to reach newborns via the current immunization service delivery system. Based on the study conducted in 2019 that highlighted the barriers and facilitators of timely birth dose administration, the Ministry of Public Health with support of CHAI decided to pilot facility specific HepB BD integration programs. A component that arose from the 2019 study that was of key concern was the lack of communication and integration between the immunization and maternity wards. Thus, this pilot work proposes a facility-based approach to better integrate birth dose vaccination into the broader facility-based maternity and newborn care processes to ensure newborns born within facilities are vaccinated within the recommended timeframe. While the previous assessment and studies have identified many common barriers to timely birth dose administration, the purpose of this work is to focus on the feasibility of integrating the birth dose vaccine process into maternity practices.

¹⁰ EPI administrative data 2018

¹¹ Chiabi A., Nguefack F., Njapndounke F., Kobela M, Kenfack K, Nguifack S., Mah E, Nguefac-Tsague G., Angwafo F., (2017). Vaccination of infants aged 0 to 11 months at the Yaounde Gynaeco-obstetric and pediatric hospital in Cameroon: how complete and how timely?. *BMC Pediatrics*. 2017. 17:206. DOI 10.1186/s12887-017-0954-1

¹² WHO (2015). A Guide for Introducing and Strengthening HepB-BD Vaccination. www.who.int/immunization/documents

2 Methodology

[figure not shown]

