2.7 Training Sessions

2.7.1 Intervention training

Training sessions will be held at each of the 15 facilities separately, with the same study members leading the sessions. Rather than a central training, we will conduct training at each facility, thus reducing mass gatherings during the COVID-19 pandemic. Please see the infection control section (Section 3.2) for COVID-19 related processes during training. At each individual training, all relevant and available health staff, including EPI focal points and maternity and newborn staff, will be asked to participate. In facilities where not all staff are able to attend training, we will ensure at least 1 staff member per shift is able to attend, to enable the information to be passed down to all staff members. During the touch points with the facility, staff will assess if the information was indeed passed down. The sessions will be split into two half day to prevent the facility from closing for a day and to allow for staff to be properly distanced. Moreover, training sessions will be held outside where possible. Ahead of training, a member of the study team will discuss potential training dates with the facility in-charge, ensuring dates occur when most convenient for the staff. The principal investigator will ensure that participants are comfortable throughout training and data collection. The training session will incorporate the below components.

Table 4: Summary of components included in training session

Training Component	Details
Maternity and newborn clinical protocols	 Knowledge reinforcement for topics relating to birth dose immunizations including: Immunization basics (Note: the HCW participating in the study are anticipated to be well-versed in this already, however we can leverage modules from Vaccination in Practice training to provide targeted refreshers based on the audience) Birth dose vaccine information for OPV0 and BCG including safety information and contraindications

	 Immunization technique including vaccine handling and site of administration Directly address hesitancy surrounding opening a multi-dose vaccine vial for only 1 baby by sharing PEV policy on opening vials for one child as well as training on practices to carry this out effectively (e.g. updating wastage rates in forecasts for ordering, calculating shelf life once opened, etc.) Reinforce incorporating birth dose conversations into routine antenatal care visits and adding messaging into ANC talking points 		

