2.10 Study Outcomes

The primary outcome of this pilot study is change in proportion of newborns receiving birth doses of BCG and OPVO within 24 hours. The key indicators from HCW surveys will be updated to include those from midline and end line surveys and will be sent for review prior to conducting those surveys.

Key Indicator	Source (data	Assessed at	Assessed at	Assessed
	collection tool)	baseline	midline	at end line
Average age of babies at time of	Birth registry and	×		×
receiving birth dose vaccines (BCG	immunization			
and OPV0)	record			
Proportion of babies born/received		×		×
in facilities receiving birth dose				
vaccines (BCG and OPV0) within 24				
hours				
The reason why BCG and OPV0 birth	Birth dose		×	×
dose vaccines were not administered	reporting form			
within 24 hours				
			×	×
			×	×
	HCW survey	×	×	×
Proportion of HCWs that know ideal		×	×	×
timing for birth dose vaccines				

Table 5. List of key indicators and sources

	×	×	×
Reported concerns with administering birth dose vaccines	×	×	×
within 24 hours			
Reported barriers to administering	×	×	×
birth dose vaccines within 24 hours			
Reported barriers to educating	×	×	×
caregivers on birth dose vaccines			
Maternity unit's access to birth dose	×	×	×
vaccines			

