2.11 Data Analysis

All outcomes will be descriptive in nature with the intent to assess preliminary impact and not statistically significant findings. For both measures of timing of birth dose vaccines, we will compare the facility-level value at baseline to end line of the intervention. Basic statistics (means and proportions) will be performed on the HCW surveys and the new birth dose reporting forms. Information and recommendations reported in open-ended questions from HCW surveys may inform final recommendations of the project but only at an aggregated level and would not be published, shared, or reported at the individual level.

To identify indications of COVID-19 impacting in-facility births, we will use the information contained in the DHIS2 over the last 2 years to compare historical yearly birth trends for the 15 included facilities, with the trends we observed during this pilot study. Due to the small sample size of health facilities and short nature of this study any potential findings of changes in time trends will be descriptive in nature. During check-ins with the facilities the team will also document other factors due to the pandemic that may impact the study such as stock outs or changes on guidance. As this data is not formally gathered, this will be documented and descriptive in nature. Please refer to study tool "Notes for touch point calls" in Section 5.4 that will gather informal information about the health facility-specific processes.

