For sampling interval, count how many children are entered within a year of today's date. Divide this total number by 30 to get your sampling interval. For instance, if there are 300 children within the year, your sampling interval is 300/30 or 10. Therefore, you will enter every 10th child until you reach 30 children in total. For this work you will also be looking the child up in the immunization register. Please ask the in-charge and the EPI nurse to gather this information when it is not in use.

	Delivery register			Immunization register									
Child Name	Q1. Date of Birth	Q2. Date of OPV0 administered	Q3. Date BCG administered	Q4. Were you able to find this child based on name	Q5. Date of OPV0 administered	Q6. Date BCG administered							
	A - Date of birth listed? 1 = Yes, 2 = No (If no, skip Q1.B)	A – Was vaccine administered? 1 = Yes, 2 = No (If no, skip Q2.B)	A – Was vaccine administered? 1 = Yes, 2 = No (If no, skip Q3.B)	and birth date in the register? 1 = Yes, 2 – No (if no, skip Q5 and Q6)	A – Was vaccine administered? 1 = Yes, 2 = No (If no, skip Q5.B)	A – Was vaccine administered? 1 = Yes, 2 = No (If no, skip Q6.B)							
	B - Date listed C – Time of Birth	B - Date listed C – Time of vaccine administration	B - Date listed C – Time of vaccine administration		B - Date listed C – Time of vaccine administration	B - Date listed C – Time of vaccine administration							

Newborn data tool

This form should be used to record data about each delivery during the study period. Data should be completed by a delivery nurse and shortly after the baby is discharged.

Child #:	Facility		Date:	//
	Code:			

Delivery Inform	nation	OPV0→	
Gender	Male1 Female2	OPV0	Yes1 No2
Date of birth, Time of birth, and birth weight	/ : : (DD/MM HH:mm) Grams	DATE AND TIME THE BABY RECEIVED OPVO	/ : : (DD/MM hh:mm)
CIRCLE ALL SERVICES PROVIDED	EPI visitA Dr visitB PNCC OtherX If other, specify:	IF NO, PLEASE CIRCLE THE PRIMARY REASON	Caregiver refused1Stock out2Scheduled for later3EPI was not open4Left before receiving the vaccine6Too few children to open a vial7Not eligible for clinical reasons8Not enough time for vaccination9Other10If other, specify:
OXYTOCIN GIVEN?	Yes1 No2	BCG→	
DISCHARGE DATE AND TIME	/ :	BCG	Yes1 No2
PLEASE LIST ANY CC	MPLICATIONS OR COMMENTS ON THE BIRTH:	DATE AND TIME THE BABY RECEIVED BCG	/ ::
		IF NO, PLEASE CIRCLE THE PRIMARY REASON	Caregiver refused

Notes for touchpoint calls

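### On the newborn form, the single primary-reason item for OPV0 mixes what happened with why, so causes of missed birth doses may be undercounted

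*Combined protocol and SAP*

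**What the plan says.** The Newborn data tool in Section 5.3 is completed for each delivery. It asks separately about OPV0 and BCG. If the answer is no, the instruction is "IF NO, PLEASE CIRCLE THE PRIMARY REASON". The legible OPV0 list covers caregiver refusal (1), stock out (2), deferral to another time (3), the immunization unit being closed (4), departure before vaccination (6), too few children for a vial (7), clinical ineligibility (8), lack of time (9) and a free-text other (10). On timing, the tool says: "Data should be completed by a delivery nurse and shortly after the baby is discharged".

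The Table 5 row in Section 2.10 that begins "The reason why BCG and OPV0 birth" takes its data from the birth dose reporting form, at midline and end line. Section 2.11 gives the analysis: "Basic statistics (means and proportions) will be performed on the HCW surveys and the new birth dose reporting forms". The indicator serves Objective 4 in Section 1.2, which is in part to "describe any factors (barriers and enablers) that may influence further implementation of birth dose strategies".

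Two barriers named in the plan bear on this list. Section 1.3 says that "most health facilities do not administer vaccines every day, but rather only on designated immunization days". The training in Section 2.7.1 is to "Directly address hesitancy surrounding opening a multi-dose vaccine vial for only 1 baby".

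**The concern.** A list that allows one answer works when its entries exclude each other or when a rule says which entry wins. This list does neither. Codes 3 and 6 describe the baby's status when the form is filled in. Codes such as 4 and 7 describe what stood in the way. A baby can have both a status and a cause, and the form keeps only one of them.

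What is at stake is the per-baby count of causes. After the intervention, the team will want to know how often a closed session or reluctance to open a vial still stopped a dose. Each baby entered under 3 or 6 drops out of that count, and a table of proportions cannot bring the cause back.

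**Working it through.** No figure in the plan can be reproduced here. The documents give no counts by code and no miscoding rate. The check is therefore a comparison of the form with the indicator it feeds. I take the Newborn data tool to be the birth dose reporting form named in Section 2.9.2 and Table 5, because it is the only per-birth form shown.

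**Step 1: do the codes exclude each other?** Three ordinary situations, read against the OPV0 list:

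| Situation | Status code that is true | Cause code that is also true |
|---|---|---|
| Told to return because the immunization unit was closed | 3 | 4 |
| Told to return because too few children were present | 3 | 7 |
| Discharged undosed because staff had no time | 6 | 9 |

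In each row two codes are correct and one may be circled.

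**Step 2: is there a rule for choosing?** None appears on the form. Section 2.7.1 says that ways of completing the form will be discussed in training, but states no order of precedence. The word primary helps only if staff take it to mean the underlying cause.

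**Step 3: are the status codes easy to choose?** The form is completed after discharge. By then an undosed baby has left without the vaccine, so code 6 can be literally true whatever the cause. Deferral is also plausible for most babies: Section 1.3 puts coverage at 84% (BCG) and 79% (OPV0), while the 2019 study in Section 1.1 found 4% and 7% vaccinated within 24 hours. The populations differ, but later vaccination is clearly common, so code 3 is a truthful answer that does not say why.

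**Step 4: which way does the error run?** Let p be the share of undosed babies whose main cause is a given barrier, and m the fraction of those entered under 3 or 6. The form then shows

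q = p × (1 − m).

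If m = 0, q = p and there is no loss. If m > 0, q is below p. To show the scale on assumed values only: with p = 40%, m = 10% gives 40% × 0.9 = 36%, and m = 50% gives 40% × 0.5 = 20%. The documents support no particular p or m. The formula covers loss to codes 3 and 6 only; confusion between two causes could move a single code either way.

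**Step 5: can another source restore the count?** The health care worker survey aims for at least 3 workers per facility (Section 2.9.3). It asks about challenges in an open question (CA7), about vial opening (B4, B5) and about access to vaccines (CA17, CA18). These give opinion, knowledge and availability. The touchpoint notes are informal (Section 2.11). None counts causes per missed dose.

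**The case against.** The best defence is that the form asks for the primary reason and gives closed sessions and vial opening their own codes. A nurse who understands the question can circle 4 or 7. Training covers how to fill in the form, photographs of the forms reach the study team every two weeks with a follow-up call (Section 2.8), and heavy use of code 3 could be noticed and queried. Codes 3 and 6 are themselves informative in an integration pilot, since deferral and early departure are workflow failures. The form also has discharge time and a comments field. All of this stands, and it lowers the risk. It does not give the form a rule or recover the cause for a baby already entered under 3 or 6.

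Five stronger readings are tempting and are not supported:

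- A reader might infer that the causes will be undercounted. The documents show only that they can be; consistent coding of the underlying cause would avoid it.
- A reader might infer that the indicator says nothing about session days or vial opening. If codes 4 and 7 are circled correctly, they still give a minimum.
- A reader might try to bound vial opening from above by adding codes 3 and 6 to code 7. That is not a true upper bound, because a baby coded 4 may also have lacked enough children for a vial, and the plan has no shares to add.
- A reader might worry that differences between facilities would reflect coding habits. Section 2.11 plans facility-level comparison for the two timing measures and not for reasons.
- A reader might treat session days and vial opening as the pilot's main targets. Vial opening is addressed in training and session days are described as a challenge, but the key concern in Section 1.3 is poor communication and integration between wards.

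The BCG list is cut off in the available text, so the overlap is shown for OPV0 only.

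A separate gap also remains. The reason is asked only when the answer is no. A baby dosed after 24 hours and marked yes gives no reason, although the Table 5 row concerns doses not given within 24 hours.

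**Conclusion.** The point holds as a risk in the design of the form. The OPV0 item takes one answer from a list that mixes status with cause, without a precedence rule, so a form completed as instructed can lose the information that the reasons indicator is meant to report. Causes such as closed sessions or vial opening may be undercounted on this form. For loss to codes 3 and 6 the direction is downward. The size is not fixed by the documents and runs from zero upward with the fraction entered under those codes.

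The reach is limited. This is one descriptive indicator serving Objective 4. The primary outcome, the change in the proportion vaccinated within 24 hours, comes from the registers and is not touched. The conclusion rests on the OPV0 list as legible and on the Newborn data tool being the form that Table 5 cites. It is worth correcting because the correction is cheap.

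**What to change.** For each vaccine, replace the single item with two:

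1. Status, one answer: scheduled for later, left before the vaccine, or neither.
2. Reason, always completed when the vaccine was not given: circle all that apply from the cause codes (refusal, stock out, immunization unit closed, too few children for a vial, clinical ineligibility, lack of time, other with detail), and mark one of those circled as primary.

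Report two percentages per reason among undosed births: the share with it as primary and the share with it circled at all. Keeping the primary mark matters, because circling all that apply would by itself lose the ranking of causes. Add one line to the form training saying that status is never a reason.

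The cost is a reprinted and slightly longer form, some seconds more per undosed baby, and any-reason percentages that can sum to more than 100%, which the report should state. The format is already familiar: the same form lets staff circle all services provided, and survey items E1 to E3 accept several answers. Section 2.7.2 already plans to pilot the tools in 2 facilities and incorporate edits, so the change can be tested there.

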5.4 Project Timeline

The study will commence after all relevant stakeholders have aligned on the project and any necessary administrative and ethical approvals for the protocol have been obtained and data collectors have been identified and trained.

Activities								We	eek											
	1	2	3	4	5	6	7	8	9	1 0	1 1	1 2	1 3	1 4	1 5	1 6	1 7	1 8	1 9	2 0
Baseline Assessment																				
Facility visits to collect baseline data	x	x																		
Conduct baseline surveys with HCWs	x	x																		
Preliminary analysis to determine current timing of birth vaccines			x	x																
Intervention implementation																				
Carry out on-site training for health facility staff					x															
Support any adjustments needed to service delivery processes (e.g. adjusting cold chain storage, etc.)					x															
Carry out twice monthly mentorship meetings to monitor progress and troubleshoot as needed							x		x				x		x					
Conduct mid-point surveys with HCWs											x									
Final assessment																				
Collect final data on timing of birth dose vaccine administration																	x			
Conduct final surveys with HCWs																	x			
Data analysis																	х	х		
Technical report development																		х	х	х

